Participants will be randomized in a 1:1 ratio to dupilumab or placebo. The randomization will be first stratified by age (adults versus adolescents) with at least 4 adolescents. Then in adult's randomization will be stratified further by country and background H1-antihistamine regular/daily use (Yes/No). Randomization will not be stratified further in adolescents.

Number of participants using H1-antihistamine as needed prior to study entry should be at least █.

- **Analysis population**

The primary analysis population for the efficacy endpoints will be the randomized intent-to-treat population which includes all participants who have been allocated to a randomized treatment regardless of whether the treatment kit was used or not. The efficacy analyses will be conducted according to the treatment to which they were randomized.

The analysis population for safety endpoints is defined as all randomized participants exposed to study medication, regardless of the amount of treatment administered. The safety analyses will be conducted according to the treatment participants actually received.

- **Primary analysis**

The primary efficacy endpoint is the proportion of participants with negative ice cube provocation test at Week 24. The statistical hypothesis for comparing dupilumab against placebo on the primary endpoint is:

- Null hypothesis H0: No treatment difference between dupilumab and placebo.
- Alternative hypothesis H1: There is a treatment difference between dupilumab and placebo.

The primary efficacy endpoint will be analyzed using the Cochran-Mantel-Haenszel test stratified by region and background H1-antihistamine regular/daily use (Yes/No). The comparison of the proportions of participants with negative ice cube provocation test at Week 24 between dupilumab and placebo will be derived, and the corresponding odd ratios and the 95% confidence interval (CI) will be reported. Participants who receive highly influential prohibited medications and/or highly influential rescue medications (details of selection will be specified in the statistical analysis plan [SAP]) will be considered as having positive ice cube provocation tests for time points after the

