1 INTRODUCTION

1.1 STUDY DESIGN

The EFC16720 study is a 24-week, randomized, double-blind, placebo-controlled, parallel-group, multi-center study to evaluate the use of dupilumab in adults and adolescents (≥ 12 to < 18 years old) with primary acquired chronic inducible cold urticaria (ColdU) who remain symptomatic despite the use of H1-antihistamine treatment. The study is designed to test the hypothesis that dupilumab will increase the proportion of participants with a negative ice cube provocation test at Week 24 compared with placebo. A negative ice cube provocation test is defined as the absence of a confluent hive/wheal at the entire skin site of exposure after an ice cube provocation test.

The study consists of 3 periods:

- Screening period (2 to 4 weeks).
- Randomized IMP treatment period (24 weeks).
- Post IMP treatment period (12 weeks).

Chronic inducible ColdU signs and symptoms will be evaluated after the ice cube provocation test, by the Investigator (hives/wheals intensity) and participant (itch severity, skin pain, skin sensation). In addition, chronic inducible ColdU disease activity will be assessed daily by the participant using ColdUAS questionnaire in an e-diary where the participant will report his/her skin reactions (wheals and swelling), skin sensations (itching, burning, pain or feeling hot), if they have been in contact with cold temperatures that usually cause skin reactions, if they have avoided trigger exposure, and overall symptoms severity. The study will also assess the effect of dupilumab on urticaria control, participants' HRQoL and overall health status, proportion of patients with cold urticaria requiring emergency medical care visit or treatment with epinephrine and on reduction of rescue therapy.

The total anticipated number of participants randomized in the study is 78. This corresponds to approximately 39 participants who will be randomly assigned to each intervention arm:

- Dupilumab: 300 mg every q2w for adults; 200 mg q2w for adolescents ≥ 30 kg and < 60 kg at baseline or 300 mg q2w for adolescents ≥ 60 kg at baseline.
- Matched placebo.

At least 4 participants randomized in the study will be adolescents (≥ 12 to < 18 years old) who will be recruited in a few selected sites in selected countries. Randomization will be stratified by age (adolescent versus adult) and within adult group by country and background H1-antihistamine regular/daily use (Yes/No).

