Routine doses of doxepin (daily or every other day during 5 or more consecutive days).		No
LTRAs and H2 receptor antagonists, unless stable and taken for diseases other than chronic inducible ColdU.		Yes for LTRAs; No for H2 receptor antagonists (SDG Leukotriene receptor antagonists for obstructive airway diseases Narrow)
Antifibrinolytic tranexamic acid and epsilon-aminocaproic acid		No
Phototherapy, including tanning beds.		No
Additional H1-AH up to 4-fold (2-fold in Japan)	No IMP discontinuation	No
Corticosteroids		Yes (SDG Corticosteroids Narrow excluding where Route is Topical, Nasal, Respiratory (Inhalation) or Ophthalmic)

a When yes, if confirmed through blinded medical review that the medication use was due to treatment failure instead of an unrelated condition, the estimand for the intercurrent event handling strategy will be as follows: composite for continuous and responder endpoints. Otherwise, a treatment policy strategy will be applied.

The intercurrent event handling strategy for the primary estimand is the treatment policy/composite approach.

The primary efficacy endpoint will be analyzed using the Cochran-Mantel-Haenszel test stratified by region (combined countries) and background H1-antihistamine regular/daily use (Yes/No). The comparison of the proportions of participants with negative ice cube provocation test at Week 24 between dupilumab and placebo will be derived, and the corresponding odd ratios and the 95% confidence interval (CI) will be reported. Participants who receive highly influential prohibited medications and/or highly influential rescue medications (see [Table 4](#)) will be considered as having positive ice cube provocation tests for time points after the medication usage. For other participants, all available data including those collected during the off-treatment period will be used to determine the positive/negative ice cube provocation test outcome. Participants with missing ice cube provocation test data at Week 24 will be considered as having positive ice cube provocation tests.

The following is a sample code for the primary analysis.

```
proc freq data=dataice;  
  tables region*background*trtgrp*response/relrisk cmh;  
  weight Count;  
run;
```

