4.4.1.2 Main analytical approach

The intercurrent event handling strategy for the key secondary endpoints is the treatment policy/composite approach.

This key secondary endpoints will be analyzed using an analysis of covariance (ANCOVA) model with baseline value of the endpoint, treatment group, region (combined countries), and background H1-antihistamine regular/daily use (Yes/No) as covariates, with intercurrent events and missing data being handled by a hybrid method of the worst-observation carried forward (WOCF) and multiple imputation. For participants who took highly influential prohibited medications and/or highly influential rescue medications (see [Table 4](#)), their data after the medication usage will be set to missing, and worst post-baseline value on or before the time of the medication usage will be used to impute missing Week 24 value (for participants whose post-baseline values are all missing, the baseline will be used to impute). Participants who discontinue the treatment prematurely are encouraged to follow the planned clinical visits. For participants who did not take the highly influential prohibited medications and/or highly influential rescue medications, all data collected after treatment discontinuation will be used in the analysis. For participants who discontinue study intervention due to lack of efficacy, all data collected after discontinuation will be used in the analysis, and a WOCF approach will be used to impute missing Week 24 value if needed (i.e., due to study discontinuation). For participants who discontinue study intervention not due to lack of efficacy, all data collected after discontinuation will be used in the analysis, and a multiple imputation approach will be used to impute missing Week 24 value if needed (i.e., due to study discontinuation). This multiple imputation will use all participants excluding participants who have taken the highly influential prohibited medications and/or highly influential rescue medications on or before Week 24 and excluding participants who discontinue due to lack of efficacy on or before Week 24. Each of the imputed complete data will be analyzed by fitting an analysis of covariance model as described above. Statistical inference obtained from all imputed data will be combined using Rubin's rule. Descriptive statistics including number of participants, mean, standard error, and least squares (LS) mean changes (and standard error) score will be provided. In addition, difference of the dupilumab group against placebo in LS means and the corresponding 95% confidence intervals (CI) will be provided along with the p-values.

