5.3 APPENDIX 3 DEMOGRAPHICS AND BASELINE CHARACTERISTICS, PRIOR OR CONCOMITANT MEDICATIONS

Demographics, baseline characteristics, medical surgical history

The following demographics and baseline characteristics, medical and surgical history and disease characteristics at baseline will be summarized using descriptive statistics in the randomized population.

Demographic variables are

- Age in years (quantitative and qualitative variable: 12-<18, 18-<40, 40-<65, 65-<75 and ≥ 75 years),
- Gender (Male, Female),
- Race (White, Black or African American, Asian, American Indian or Alaska Native, Native Hawaiian or other Pacific Island, unknown),
- Ethnicity (Hispanic or Latino, Not Hispanic or Latino, Unknown)
- Region (**Asia**: Japan; **Latin America**: Argentina; **Western Countries**: Canada, USA, Germany)
- Weight in kg (quantitative and qualitative variable: <60, ≥ 60 kg)
- BMI in kg/m² (quantitative and qualitative variable: <30, ≥ 30 kg/m²)

Baseline safety and efficacy parameters (apart from those listed above) will be presented along with the safety and efficacy summaries.

Medical (or surgical) history includes all the relevant medical (or surgical) history during the lifetime of the participant.

This information will be coded using the version of MedDRA currently in effect at Sanofi at the time of database lock.

Comorbidity will be summarized separately. The following comorbid diseases will be summarized from electronic case report form (eCRF) pages which were filled in by investigators based on participant reporting. Angioedema history will be further summarized under disease characteristics at baseline.

CSU (Yes, Ongoing condition)

Atopic Dermatitis (Yes, Ongoing condition)

Allergic rhinitis (Yes, Ongoing condition)

Allergic Conjunctivitis (Yes, Ongoing condition)

Asthma (Yes, Ongoing condition)

Food allergy (Yes, Ongoing condition)

Chronic Rhinosinusitis (Yes, Ongoing condition)

Nasal Polyps (Yes, Ongoing condition)

Eosinophilic Esophagitis (Yes, Ongoing condition)

Disease characteristics at baseline

The following baseline disease characteristics will be summarized by intervention group:

- Age at onset of cold urticaria (years)
- Duration of cold urticaria before screening visit (years) to be derived as
- (Year of screening visit – Year of first diagnosis of cold urticaria) + (month of screening visit-month of first diagnosis of cold urticaria)/12

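### Age is the first randomisation factor but is missing from the primary CMH test and the ANCOVA; aligning them is a cheap improvement with a small effect either way

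*SAP*

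**What the plan says.** **Randomisation.** SAP 1.1: "Randomization will be stratified by age (adolescent versus adult) and within adult group by country and background H1-antihistamine regular/daily use (Yes/No". The protocol synopsis gives the order and the minimum number: "The randomization will be first stratified by age (adults versus adolescents) with at least 4 adolescents". It adds: "Randomization will not be stratified further in adolescents". Protocol 4.1 and 6.3 describe the same scheme. No upper limit on adolescents is given.

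**Primary analysis.** SAP 4.3.2: "The primary efficacy endpoint will be analyzed using the Cochran-Mantel-Haenszel test stratified by region (combined countries) and background H1-antihistamine regular/daily use (Yes/No". The analysis is in the ITT population, which includes adolescents. The sample code has the same two factors and no age term: "tables region*background*trtgrp*response/relrisk cmh". SAP 5.3 defines three regions: Japan, Argentina, and a Western group ("Canada, USA, Germany"). That gives 3 x 2 = 6 cells.

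**Continuous endpoints.** SAP 4.4.1.2 specifies an "analysis of covariance (ANCOVA) model with baseline value of the endpoint, treatment group, region (combined countries), and background H1-antihistamine regular/daily use (Yes/No) as covariates". Age is absent here too.

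**Elsewhere.** The tipping-point analysis (SAP 4.3.3) uses the same two factors in its logistic model (Step 1) and in its CMH test (Step 4). Adult v adolescent appears only as a subgroup factor, with an interaction model, for the primary endpoint (SAP 4.3.5). Protocol 9.4.1 and 10.13 plan the same models. We found no reason given for leaving age out.

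**The concern.** The usual principle is to analyse by the factors used to randomise. Here two of the three factors are carried into the analysis, with country collapsed to region, and the first is dropped. Adolescents were balanced between arms as one group, not within region by H1-antihistamine cells, but the CMH compares them within those cells.

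If adolescents respond differently from adults, stratified randomisation removes variation between arms that the planned test still counts in its variance. The test then rejects slightly less often than its nominal level and loses some power. What is at stake is efficiency at a two-sided alpha of 0.01 with 78 participants, and a settled choice of strata before unblinding.

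**Working it through.** **1. Inputs from the documents.** N = 78, 39 per group, 1:1; two-sided alpha 0.01; 90% power; 10% drop-out; unpooled Z test (SAP 2, 4.6). At least 4 adolescents, that is 4/78 = 5%. Missing Week 24 tests count as positive (SAP 4.3.2). Both response rates are redacted.

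**2. The plan's own figure.** With the unpooled formula

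n = (z0.995 + z0.90)² x [p1(1-p1) + p2(1-p2)] / (p1-p2)²

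and assumed rates of 15% v 55%: (2.576 + 1.282)² x (0.1275 + 0.2475) / 0.16 = 14.88 x 0.375 / 0.16 = 34.9, so 35 evaluable. Then 35/0.9 = 38.9, so 39 per group. Other pairs (5% v 40%, 10% v 48%, 25% v 67%, 30% v 72%) also give 39. The stated size is therefore coherent, but it does not identify the rates.

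**3. Simulation of the planned design.** Assumptions not in the documents: blocks of 4, country shares, 60% regular H1-antihistamine use, 4, 8 or 12 adolescents, an adolescent log-odds shift of 0 or 1.5, and null rates of 15% or 30%. A shift of 1.5 moves a 15% rate to about 44% (odds 0.176 x 4.48 = 0.79; 0.79/1.79 = 0.44). The test statistic is

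[Σ(a - n1·r/n)]² / Σ[n1·n0·r(n-r) / (n²(n-1))], summed over strata, rejecting above 2.576² = 6.63.

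Here a is responders on dupilumab, r all responders, n1 and n0 the arm sizes, and n the stratum size.

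Power at 15% v 55% (4,000 trials each; Monte Carlo error √(0.8 x 0.2/4000) = 0.6 points per figure; all tests run on the same trials):

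| Adolescents | Shift | SAP, 6 strata | 7 strata | Change (points) | Full age x region x H1 cross |
|---|---|---|---|---|---|
| 4 | 0 | 82.2% | 82.4% | +0.2 | 80.3% |
| 4 | 1.5 | 80.1% | 80.8% | +0.6 | 79.5% |
| 8 | 0 | 83.2% | 83.1% | -0.1 | 80.6% |
| 8 | 1.5 | 79.4% | 80.6% | +1.2 | 79.1% |
| 12 | 0 | 81.1% | 81.4% | +0.3 | 79.1% |
| 12 | 1.5 | 78.4% | 80.5% | +2.1 | 78.8% |

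Type I error (8,000 trials; Monte Carlo error about 0.001) is 0.007 to 0.011 for both the 6- and 7-stratum tests. With the age shift it is 0.0068 to 0.0075 for the SAP test and 0.0084 to 0.0095 for seven strata. That is the slight conservatism expected.

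**4. When region and H1-antihistamine use are prognostic.** With log-odds effects of 1.5 and 1.0 for these factors and none for age (6,000 trials each), seven strata change power by -0.1, -0.5 and -0.5 points for 4, 8 and 12 adolescents.

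**5. Age in the tipping-point logistic model.** The age coefficient cannot be estimated if all observed adolescents have the same result. With 4 adolescents split 2:2 and rates of 15% v 55%, the chance is 0.85² x 0.45² + 0.15² x 0.55² = 0.146 + 0.007 = 0.153. Simulated scenarios gave 9% to 18%.

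**The case against.** **The benefit depends on an age effect that the documents do not establish.** Protocol 4.2 describes the disease as similar in adults and adolescents in pathophysiology, presentation and diagnosis. Only the minimum of 4 adolescents is documented; 8 and 12 are assumptions. This stands, and it limits the expected gain. A reader might infer a larger benefit: simulation with a 35-point effect and a baseline response of 50% in adolescents v 15% in adults gives 74.5% to 78.5% power with 12 adolescents. Those rates imply an odds ratio of 1.0/0.176 = 5.7, for which the documents give no basis.

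**The change is not free.** Adolescents leave the region and H1-antihistamine adjustment, and the sign of the effect depends on which factor is prognostic. This stands (step 4), although the possible loss is small.

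**Seven strata still do not reproduce the randomisation exactly**, because adults are randomised by country and analysed by region. True, but pooling sparse countries is a stated choice, whereas the omission of age is not explained.

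**Age is covered by a subgroup analysis.** It is, but that does not change the confirmatory test.

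**Adding age everywhere could do harm.** This stands for the tipping-point logistic model (step 5) and for DLQI. DLQI is analysed only from age 16, so the adolescent group there could have almost no members.

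**Conclusion.** The mismatch is plain in the text and the code, and its consequence is small. Under assumed rates of 15% v 55%, aligning the analysis changes power by about -0.5 to +2 points. With 4 adolescents the change is near zero unless response differs strongly by age. The power figures are for the CMH only; no corresponding calculation was made for the ANCOVA.

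Three stronger readings are not supported:

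- That the primary test is invalid or inflates type I error. Simulated error stays near or below 1%, and the primary conclusion is not threatened.
- That the SAP departs from the protocol. The protocol plans the same models.
- That the trial is underpowered because simulated power is near 80%. That level reflects the assumed rates, drop-outs counted as positive tests, and the CMH variance. It is not evidence on this point.

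**What to change.** Before database lock:

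- **CMH:** use seven strata, with adolescents as one stratum and adults by region (3) x H1-antihistamine use (2). Use the same strata in Step 4 of the tipping-point analysis.
- **ANCOVA:** add an age-group covariate (adolescent/adult) for endpoints analysed in all participants.
- **Leave alone:** the tipping-point logistic model when adolescents are very few, and the DLQI model. Do not fully cross age with region and H1-antihistamine use; in step 3 the cross ran from 2.6 points below the planned test to 0.4 points above it.

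If the sponsor prefers to keep the planned strata, one sentence explaining why age is omitted, with the seven-stratum CMH as a sensitivity analysis, would be enough.

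**Cost.** No new data or participants. The edits touch the SAP 4.3.2 text and code, 4.3.3 Step 4, 4.4.1.2 and the estimand table (Table 2). The departure from the protocol model must be recorded in SAP Appendix 2. The statistical price is up to about 0.5 points of power if region and H1-antihistamine use are prognostic and age is not.

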4.3.3 Sensitivity analysis

The following sensitivity analyses will be performed targeting the same estimand as in the primary analysis to assess the impact of other missing data handling strategies. In the primary analysis, participants with missing ice cube provocation test data at Week 24 will be considered as having positive ice cube provocation tests.

Tipping point analysis

A tipping point analysis will be performed for the primary endpoint with imputed missing Week 24 values as follows:

- **Step 1.** With the complete data, fit a logistic regression model with the ice cube provocation test result (1: negative, 0: positive) at Week 24 as outcome and treatment group, region (combined countries), and background H1-antihistamine regular/daily use (Yes/No) as covariates.
- **Step 2.** Compute the probability of having negative ice cube provocation test for the participant with missing Week 24 value in placebo group from the fitted model but with the coefficient of the treatment group being added by a constant d . At the same time, compute the probability of having negative ice cube provocation test for the participant with missing Week 24 value in dupilumab group from the fitted model but with the coefficient of the treatment group being subtracted by a constant p .
- **Step 3.** With the probabilities computed in **Step 2**, impute the missing ice cube provocation results at Week 24 by generating binary random variables with the corresponding probabilities. Repeat this process to generate 40 imputed datasets.

- **Step 4.** Apply the Cochran-Mantel-Haenszel test stratified by region and background H1-antihistamine regular/daily use (Yes/No) for each imputed dataset. The results obtained from multiple imputed datasets will be combined to generate statistical inference, i.e. p-value and treatment difference between 2 treatment groups. Then use the SAS MIANALYZE procedure to generate statistical inferences of the odds ratios by combining results from the 40 analyses using Rubin's formula.

Step 2 to Step 4 will be repeated iteratively until the p-value for treatment effect of dupilumab compared to placebo estimated is >0.01 .

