- If the participant misses more than 2 consecutive doses of the IMP (see [Section 7.1.2](#)).
- Systemic hypersensitivity reaction including anaphylaxis related or suspected to be related to ice cube provocation test. In the participants who experienced such reaction no further ice cube provocation test should be done during the study.

See the SoA ([Section 1.3](#)) for data to be collected at the time of intervention discontinuation and follow-up and for any further evaluations that need to be completed.

Any abnormal laboratory value or ECG parameter will be immediately rechecked for confirmation within a reasonable timeframe as assessed by the Investigator before making a decision of definitive discontinuation of the IMP for the concerned participant.

If a clinically significant ECG finding is identified (including, but not limited to changes from baseline in QT interval corrected using [Bazett's formula {QTcB} or Fridericia's formula {QTcF}]) at screening, the Investigator or qualified designee will determine if the participant is eligible for the study. This review of the ECG printed at the time of collection must be documented. Any new clinically relevant finding should be reported as an AE.

Handling of participants after definitive intervention discontinuation

Participants will be followed-up according to the study procedures specified in this protocol up to the scheduled date of study completion, or up to recovery or stabilization of any AE to be followed-up as specified in this protocol, whichever comes last.

Participants who discontinue the study intervention prematurely (prior to completing the 24-week treatment period) will perform, as soon as possible, the early treatment discontinuation Visit with all assessments normally planned for the EOT visit (Visit 4), to assure a complete clinical assessment in close temporal proximity to the premature termination of study treatment is available.

In addition, and to allow assessment of participant outcomes over the stipulated study period, participants will be asked and encouraged to complete all remaining study treatment visits and participate in safety follow-up according to the visit schedule with a ± 3 day window. Under exceptional circumstances when a participant cannot come to the study center for a scheduled visit, a phone contact can be made. During the phone contact, at least information about AEs, concomitant medication and status of urticaria should be collected.

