9.4.1 Efficacy analyses

Statistical analysis methods for the primary, secondary, and tertiary/exploratory endpoints are presented in the table below ([Table 7](#)). In addition, for the primary and secondary endpoints, the primary estimand and details about the intercurrent events strategy and missing data handling are presented in Appendix 13 ([Section 10.13](#)).

Table 7 - Efficacy analyses

Endpoint	Statistical analysis methods
Primary	
Primary endpoint: Proportion of participants with negative ice cube provocation test at Week 24	
The primary efficacy endpoint will be analyzed using the Cochran-Mantel-Haenszel test stratified by region and background H1-antihistamine regular/daily use (Yes/No). The comparison of the proportions of participants with negative ice cube provocation test at Week 24 between dupilumab and placebo will be derived and the corresponding odd ratios and the 95% confidence interval (CI) will be reported. Participants who receive highly influential prohibited medications and/or highly influential rescue medications (details of selection will be specified in the statistical analysis plan [SAP]) will be considered as having positive ice cube provocation tests for time points after the medication usage. For other participants, all available data including those collected during the off-treatment period will be used to determine the positive/negative ice cube provocation test outcome. Participants with missing ice cube provocation test data at Week 24 will be considered as having positive ice cube provocation tests.
 
Sensitivity analysis
 
Tipping point analyses and other sensitivity analyses will be performed to confirm robustness of the results with respect to the missing data handling. Details of the sensitivity analyses will be provided in the SAP.
 
Subgroup analysis
 
To assess the consistency in treatment effects across different subgroup levels, subgroup analyses will be performed for the primary efficacy endpoint with respect to age group, gender, region, and other factors that will be specified in the SAP.

Secondary	

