2 SAMPLE SIZE DETERMINATION

Sample size is calculated based on the following assumptions:

1. The placebo group has █ participants with negative ice cube provocation test at Week 24 and the dupilumab group has █ participants with negative ice cube provocation test at Week 24.
2. There is a drop-out rate of 10% in both groups.
3. The statistical test is a Z test that is based on the difference of the 2 proportions with unpooled variance estimate and 2-sided 1% significance level.
4. Participants are equally randomized to the dupilumab group and the placebo group.

With these assumptions, 39 participants per group (78 participants in total) will provide 90% power to detect the difference of █ response rate in the dupilumab group and █ response rate in the placebo group. The sample size calculations were performed using nQuery+nTerim 4.0.

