4.3.4 Supplementary analyses

The following supplementary analysis will be performed:

As-observed analysis (Including all data after taking highly influential prohibited medications and/or highly influential rescue medications)

The data collected after taking the highly influential prohibited medications and/or highly influential rescue medications will be included in the supplementary analysis to evaluate the robustness of the primary analysis results with respect to the intercurrent event handling strategy. Missing ice cube provocation test result at Week 24 will be considered as positive.

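### The tipping-point rule for the primary endpoint does not fix what is shifted: read literally with a single treatment indicator, one arm stays put or moves the wrong way, and the loop need not end

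*SAP*

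**What the plan says.** Step 1 of the tipping-point analysis in SAP 4.3.3 fits a single logistic model for a negative ice cube test at Week 24. The covariates are treatment group, region and background antihistamine use. The outcome is coded (1 negative, 0 positive); treatment is not.

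Step 2 sets the imputation probability for a missing value "in placebo group from the fitted model but with the coefficient of the treatment group being added by a constant" d, and for a missing value "in dupilumab group from the fitted model but with the coefficient of the treatment group being subtracted by a constant" p. Step 3 draws 40 imputed datasets. Step 4 applies the stratified CMH test to each, combines the results for a p-value, and then pools the odds ratios by Rubin's formula. Steps 2 to 4 are "repeated iteratively until the p-value for treatment effect of dupilumab compared to placebo estimated is" above 0.01.

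The only sample code, in SAP 4.3.2, is for the CMH test. It names one treatment variable without its levels.

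Protocol 9.4.1 promises that "Tipping point analyses and other sensitivity analyses will be performed to confirm robustness of the results with respect to the missing data handling" and leaves details to the SAP. SAP 4.3.3 contains only this analysis. The supplementary analysis in SAP 4.3.4 keeps the primary rule: "Missing ice cube provocation test result at Week 24 will be considered as positive".

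**The concern.** Two constants, one for each arm, are applied to what the text calls the coefficient of the treatment group in one model. If that model has a single treatment coefficient, changing it cannot shift both arms in the intended directions under the usual codings. One arm then contributes nothing, or works in favour of dupilumab, and the primary result looks more robust to missing data than it is. No other planned analysis of the primary endpoint varies the missing-data rule, so nothing else would reveal this.

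A separate gap is that the search has no grid, step or upper bound, and no instruction for a result that never tips.

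**Working it through.** **Plan's own figures.** The rule states no numerical result to reproduce. The sample size of 39 per arm cannot be confirmed because both planning rates are redacted.

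**Step 1: algebra, with no assumed rates.** Write the linear predictor as a + b·x + other terms, where x is the treatment code. Replacing b by b + d for placebo and by b − p for dupilumab moves the log-odds by +d·x(placebo) and −p·x(dupilumab). The intended shifts are +d and −p. With d = p = 1:

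| Coding | Placebo shift | Dupilumab shift | Effect |
|---|---|---|---|
| One coefficient per arm | +1 | −1 | as intended |
| 0/1, dupilumab = 1 | 0 | −1 | placebo inert |
| 0/1, placebo = 1 | +1 | 0 | dupilumab inert |
| +1/−1, dupilumab = +1 | −1 | −1 | placebo reversed |
| +1/−1, placebo = +1 | +1 | +1 | dupilumab reversed |
| ±0.5, dupilumab = +0.5 | −0.5 | −0.5 | placebo reversed |
| ±0.5, placebo = +0.5 | +0.5 | +0.5 | dupilumab reversed |
| Numeric 1/2, placebo = 1 | +1 | −2 | right direction, p doubled |

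**Step 2: inputs for an illustration.**
- From the SAP: 39 per arm, 40 imputations, threshold 0.01. For drop-out, "There is a drop-out rate of 10% in both groups", so 39 × 0.10 = 3.9, about 4 missing and 35 observed per arm.
- Assumed: 5/35 negative on placebo and 19/35 on dupilumab (14% v 54%). This is close to 15% v 55%, one of several pairs that fit the stated design: (0.15×0.85 + 0.55×0.45) × (2.576 + 1.282)² / 0.40² = 34.9, so 35, and 35/0.9 = 38.9, so 39.
- Simplified: one stratum. The CMH Z (within-imputation variance 1) is pooled by Rubin's rule using the exact expected mean and between-imputation variance B, so the total variance is T = 1 + (41/40)·B.

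**Step 3: primary result, missing counted as positive.** With one stratum the CMH chi-square is (N − 1)(ad − bc)² / (product of the four margins). For 5/39 v 19/39: 77 × (5×20 − 34×19)² / (39×39×24×54) = 11.65, p = 0.0006.

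**Step 4: largest p the analysis can reach.**
- Both shifts working, extreme corner (9/39 v 19/39, so B = 0): 77 × (9×20 − 30×19)² / (39×39×28×50) = 5.50, p = 0.019. The result tips.
- Placebo shift inert (missing placebo imputed at 5/35, all missing dupilumab positive): mean Z 3.254, B 0.037, 3.254/√1.038 = 3.19, p = 0.0014.
- Dupilumab shift inert (all missing placebo negative, missing dupilumab imputed at 19/35): mean Z 2.811, B 0.045, 2.811/√1.047 = 2.75, p = 0.006.

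With either arm inert, no tipping point is found although one exists.

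**Step 5: how far one must go.** The starting log-odds are ln(5/30) = −1.79 and ln(19/16) = 0.17. At d = p = 2 the imputation probabilities become 0.55 (placebo) and 0.14 (dupilumab): mean Z 2.929, B 0.090, 2.929/√1.092 = 2.80, p = 0.005. At d = 3, p = 2 they are 0.77 and 0.14, and p = 0.0091, still below 0.01.

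**Step 6: a second illustration, including reversal.** With assumed counts 4/35 v 17/35, 4 missing per arm and the same pooled test (simulated imputations), p at d = p = 4 is 0.0226 with both shifts working. It is 0.0018 with placebo inert, 0.0010 with placebo reversed, 0.0089 with dupilumab inert and 0.0020 with dupilumab reversed.

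**Step 7: the loop.** Missing data may be fewer than 4 per arm, because after stopping treatment "participants will be asked and encouraged to complete all remaining study treatment visits". Take 5/37 v 19/37 with 2 missing per arm. The worst corner is 7/39 v 19/39: 77 × (7×20 − 32×19)² / (39×39×26×52) = 8.20, p = 0.0042. Even with correctly working shifts, p never exceeds 0.01 and the loop as written has no end.

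**The case against.** The strongest reply is that the intent is plain. Each arm has its own clause and its own constant, which makes sense only if each arm's own term is shifted. A model with one coefficient per arm does exactly that. A programmer would probably notice that placebo probabilities do not respond to d. The CMH sample code says nothing about how the logistic model is parameterised. The SAP does not restrict d and p to positive values, so under +1/−1 or centred coding a negative constant for the negatively coded arm would restore the intended direction. Open-ended iteration is common shorthand, and a trial that never tips is simply reported as robust.

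Most of this stands, and it limits the point to an under-specified rule. It does not remove it: the text does not state the per-arm reading, does not give signs for the constants, and does not say what to do when no shift tips the result. Under 0/1 coding no choice of sign rescues the inert arm.

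Two stronger readings are tempting. A reader might infer that the programmed analysis will be wrong; the documents do not show this, because a working parameterisation is compatible with the text. A reader might also infer that a significant result would often prove fragile once the rule is corrected. With the rates redacted, no such frequency can be drawn from the documents, and in the first illustration tipping requires shifts that many would call implausible.

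**Conclusion.** The point holds as an ambiguity with a known direction of error. Under each 0/1, +1/−1 or centred version in the table, taken literally with positive constants, one arm is inert or reversed and the analysis understates sensitivity to missing data. That part is algebra and rests on no assumed rates.

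The size is illustrative only: a largest p of 0.019 when both shifts work, against 0.0014 or 0.006 when one is inert. It rests on assumed counts, 4 missing per arm, a single stratum and Rubin pooling of the CMH Z. The non-ending loop is a second, independent gap.

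The primary test, the 1% alpha and the sample size are untouched. This is a clarification that should be made before database lock, not a threat to the main result.

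**What to change.** In SAP 4.3.3 Step 2, state that d ≥ 0 is added to the log-odds (linear predictor) of placebo participants with missing Week 24 data, and that p ≥ 0 is subtracted from the log-odds of dupilumab participants with missing Week 24 data. The result then no longer depends on coding.

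Replace the open loop by a finite two-way grid of d and p that reaches the corner where all missing placebo results are negative and all missing dupilumab results are positive. Report the pooled CMH p-value in every cell, and say so explicitly if no cell exceeds 0.01.

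The cost is a few lines of SAP text and code, with no extra participants or data. The reported tipping point may be less favourable, and cells near the extreme corner will still need a judgement on plausibility.
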